#### 6 PRIOR AND CONCOMITANT ILLNESSES AND TREATMENTS

#### 6.1 Medical Conditions

Additional illnesses, independent of the treated condition, present at the time informed consent is given or within 4 weeks prior to first study treatment administration must be documented in the eCRF. Relevant past illnesses (including other cancers) must also be documented in the section "Prior and Concomitant Conditions" of the eCRF.

Medical conditions first occurring or detected during the study or worsening of a concomitant illness during the study, are to be considered TEAEs and must be documented in the "Adverse Events" section of the eCRF.

#### 6.2 Medications

All treatments taken by patients at study entry or within 4 weeks or 5 half-lives prior to initiating treatment (whichever is longer) or at any time during the study, in addition to the investigational product are considered concomitant medications and must be documented in the eCRF.

No premedication is planned.

#### **Allowed**

- Supportive treatment of symptoms/AEs or standard treatment of concomitant conditions, including corticosteroids, aspirin, transfusion support, and antibiotics,
- Growth factors (G-CSF, EPO etc.) after cycle 1.
- For CRPC patients, maintenance treatment with ongoing androgen deprivation therapy with a gonadotropin releasing hormone (GnRH) analogue or antagonist is mandatory providing serum testosterone is < 50 ng/dL (<1.7 nmol/L), unless the patient had previous bilateral orchiectomy as part of his hormone therapy.
- Chemotherapy, hormone therapy or any other anticancer therapy or surgical intervention resection performed ≥ 3 weeks prior to study start (≥ 6 weeks for nitrosoureas or mitomycin C) or ≥ 3 half-lives for monoclonal antibodies or ≥ 5 half-lives for other non-cytotoxic agents (whichever is longer). Palliative radiation therapy (for analgesia) is authorized only if the irradiated field does not include target lesions.
- Bisphosphonates or denosumab given at stable doses for ≥ 4 weeks prior to study start. Bisphosphonates or denosumab are permitted from cycle 3.
- Prophylactic low-dose LMWH or antivitamin K (INR < 3); INR must be monitored in accordance with local institutional practices. Patients who develop venous thromboembolic events during study requiring therapeutic levels of LMWH must be closely monitored for their platelet counts.

#### Not allowed

- Other concurrent investigational drugs, agents or devices or any other therapy for cancer treatment.
- Any drugs given with a prophylactic intent during the first cycle.

- Concurrent treatment with strong CYP3A4 interfering drugs/substances is not permitted. The concomitant use of other CYP3A4 interfering drugs or any CYP2A6 interfering drug is allowed provided a careful follow-up of laboratory results that may be influenced by the concomitant agent is performed (e.g. INR if the concomitant agent is an anticoagulant, blood cell counts if the concomitant drug is hematotoxic must be followed up more frequently than required by the protocol). A list is provided in Appendix 3, however since this list is not comprehensive, the investigator should use his/her medical judgment when a patient presents with a medication not on the list or call the Sponsor Medical Expert for clarification.
- Current use of anticoagulants (e.g. warfarin, heparin) at curative therapeutic levels within 7 days prior to the first dose of OTX015/MK-8628, with the exception of prophylactic low-dose LMWH or antivitamin K (INR < 3).

#### 7 STUDY PROCEDURES AND SCHEDULE

# 7.1 Pre-Study Screening Visit

Each candidate patient will be examined before starting the study to determine eligibility for participation. This must be done within 2 weeks prior to the first study treatment administration, except for radiologic assessment which can have been performed up to 4 weeks prior to study start. The following investigations will be performed:

- Informed consent: obtain written patient informed consent prior to any specific study procedure
- Verification of eligibility criteria
- Demographics, medical history, including non-cancer medical history, and concurrent illnesses
- Diagnosis and prior treatment for malignancy (a confirmatory diagnosis of NUT midline carcinoma or NSCLC at screening is not required)
- Physical examination, PS (Appendix 1), vital signs (temperature, blood pressure, pulse), body weight, height
- Pregnancy test if child-bearing potential (urine test)
- Baseline symptoms and complaints
- Complete blood count (CBC), including hemoglobin, RBC counts, WBC and differential, platelet counts
- INR, Factor VII
- Serum chemistries: Na, K, Ca, Mg, P, Cl, HCO3, creatinine, total protein, albumin, glucose, alkaline phosphatase, total bilirubin, AST, ALT, LDH
- Tumor evaluation: physical examination, CT, MRI, and/or chest X-ray (PA and lateral), as indicated by the patient's diagnosis. A bone scan is mandatory for CRPC patients.
- Serum tumor markers, according to indication (PSA, CA19-9, CA15-3, CEA, etc.); as far as possible, subsequent measures must be made in the same laboratory
- Concomitant medications

# 7.2 Evaluations During Study Treatment

#### Visit: Day 1 of each cycle

For cycle 1, patients participating in pharmacokinetics will be observed for  $\geq 8$  hours after the first study drug administration to collect PK blood samples and check vital signs, when appropriate.

- Physical examination, PS, vital signs, body weight
- CBC
- INR, Factor VII
- Serum chemistries: all patients with specific liver test abnormalities (see Section 5.2.4) should be monitored weekly until all abnormalities return to normal or to the baseline state. For patients with isolated total bilirubin increases >2 x ULN or 2 x baseline (if elevated at baseline), monitoring should be every 2 weeks until bilirubin returns to normal or to the baseline state. DILI may develop or progress even after the causative drug has been stopped.
- Concomitant medications
- Adverse events
- Tumor markers, as appropriate for tumor type; as far as possible, measures must be made in the same laboratory
- Dispensing of study drug (adequate quantity until day 1 visit of next cycle)
- Day 1 of cycle 1 only: PK blood sampling in patients included in the dose escalation part of the study and selected patients from the expansion cohort (see Section 10 for full PK details): T0 (just before OTX015/MK-8628 intake), T15min (±5 min) post-dose, T1h (±15 min) post-dose, T2h (±15min) post-dose, T3h (±15min) post-dose, and T7h (±15min) post-dose
- Day 1 of every 2nd cycle (C3, C5, C7, etc.; i.e., every 6 weeks): Tumor imaging (CT, MRI, and/or chest X-ray, as indicated) and response assessment
- Day 1 every 4th cycle (C5, C9, C13 etc.; i.e., every 3 months): Bone scan for CRPC patients

Twice a week for cycles 1 and 2 then weekly thereafter

CBC

Weekly for cycles 1 and 2

- Serum chemistries; from cycle 3 on, in the absence of  $\geq$  grade 2 abnormalities these tests will be performed every cycle; otherwise they are to be done weekly until resolution to baseline levels or  $\leq$  grade 2.
- INR, Factor VII

# 7.3 End of Treatment Visit and Follow-Up

After the last treatment administration, patients will be followed up for safety for 30 days and then until resolution of any TEAEs for which a relationship to OTX015/MK-8628 cannot definitely be excluded (or categorized as sequelae).

# A visit will be performed 35 days (±5 days) after the last OTX015/MK-8628 intake, including the following:

Physical examination, PS, vital signs, body weight

- CBC
- INR, Factor VII
- Serum chemistries
- Concomitant medications
- Adverse events
- Tumor imaging
- Tumor markers

The last patient will be followed-up for at least two cycles after treatment initiation to allow for evaluation of efficacy.

#### 8 ASSESSMENT OF SAFETY

In emergency situations, the investigator should immediately contact a Sponsor representative at the telephone number or email address given on the title page of this protocol.

Patients will be monitored for signs and symptoms of AEs throughout the study by a qualified oncologist, with experience in clinical research. All AEs will be reported in the eCRF, including seriousness, NCI-CTCAE v4.03 grade severity, causal relationship to the study medication, and action taken. The first concern will be the safety of the study participant.

Incidence, severity and relationship of AEs and laboratory abnormalities, SAEs, discontinuations and dose adaptations due to AEs will be recorded.

#### 8.1 Clinical Safety

Clinical and physical examinations, as well as vital signs evaluation, will be performed. Patient data will be analyzed for evidence of cumulative toxicity with repeated cycles of therapy.

TEAEs and signs and symptoms of disease observed by the investigator (preferably by the same physician for a same patient) or reported by patients to the study nurses will be recorded and graded according to NCI-CTCAE version 4.03, accessible via internet [http://evs.nci.nih.gov/ftp1/CTCAE/CTCAE\_4.03\_2010-06-14\_QuickReference\_8.5x11.pdf]. It is crucial that all events, including those considered not related to the study drug are reported in the eCRF.

#### 8.2 Laboratory Measurements

Any laboratory abnormality assessed as related, probably related, or possibly related must be reported as a TEAE in the eCRF. Clinically significant laboratory values must be reported as TEAEs in the eCRF. Clinically significant laboratory results are those which have clinical consequences (i.e. need treatment or corrective measures, result in study drug dose reduction, delay or discontinuation, hospitalization, prolongation of hospitalization, or death, are life-threatening, are reported as an SAE whatever the reason, or are considered a toxicity of the treatment). The seriousness, the action taken regarding study medication and patient participation in the study, relation to study medication and the most likely cause, must be recorded.

#### **8.3** Definitions (21 CFR§312.32)

• Adverse event (AE) means any untoward medical occurrence associated with use of a drug in humans, whether or not considered drug related. The term treatment emergent adverse event [TEAE] covers any

unfavorable and unintended sign, symptom, syndrome, or illness that develops or worsens during the period of observation in the clinical study. Surgical or other procedures themselves are not TEAEs. The condition for which the surgery/other procedure is required, is a TEAE, if it occurs or is detected during the study period. Planned surgical or other procedures planned/permitted by the study protocol and the condition(s) leading to these measures are not TEAEs, if the condition(s) was (were) known before the start of study treatment. In the latter case the condition should be reported as medical history.

- Adverse drug reaction (ADR) means an AE caused by the drug.
- Suspected adverse reaction (SAR) means any AE for which there is a reasonable possibility that the drug caused the AE. A "reasonable possibility" means there is evidence to suggest a causal relationship between the drug and the AE. SAR implies a lesser degree of certainty about causality than an ADR, and include:
  - A single occurrence of an event that is uncommon and known to be strongly associated with drug exposure;
  - One or more occurrences of an event that is not commonly associated with drug exposure, but is otherwise uncommon in the population exposed to the drug (e.g., tendon rupture);
  - An aggregate analysis of specific events observed in a clinical trial (such as known consequences of the underlying disease or condition under investigation or other events that commonly occur in the study population independent of drug therapy) that indicates those events occur more frequently in the drug treatment group than in a concurrent or historical control group.
- Serious adverse event (SAE) or serious suspected adverse reaction (SSAR) is an event that, in the view of either the investigator or Sponsor, results in any of the following outcomes:
  - Death occurring on study or within 30 days after the last administration of study drug (regardless of relationship to study treatment) or within any interval if related to the study drug. Although death may occur as a result of the disease, all deaths occurring within 30 days of the last administration of study drug must be managed as SAEs and reported as such;
  - A life-threatening AE;
  - Inpatient hospitalization or prolongation of existing hospitalization;
  - A persistent or significant incapacity or substantial disruption of the ability to conduct normal life functions;
  - A congenital anomaly/birth defect.

In addition, medical and scientific judgment should be exercised in deciding whether expedited reporting is appropriate in situations where none of the outcomes listed above occurred. Important medical events that may not be immediately life-threatening or result in death or hospitalization but may jeopardize the patient's safety or may require intervention to prevent one of the outcomes listed in the definition above should also usually be considered serious. Examples of such events include overdose even without complications, or an AE requiring intensive treatment without hospitalization. A diagnosis of a new cancer type during the course of a treatment should be considered as medically important. In addition, any pregnancy diagnosed in a female patient on treatment with the investigational product or in the partner of a male patient on treatment with the investigational product must be reported to the Sponsor immediately. The List of Critical Terms (1998 adaptation of WHO Adverse Reaction Terminology Critical Terms List, provided in the "Instructions for completing the 'Serious Adverse Event/Expedited Report from a Clinical Trial' form") should be used as guidance for AEs that may be considered serious because they are medically important.

For the purpose of the dose-finding part of this study, any suspected DLT occurring during the dose escalation part will be considered as medically important and reported as an SAE even if it does not meet other criteria for seriousness. In the latter case, the reason for seriousness will be "other important medical event".

- Life-threatening AE or life-threatening SAR is an AE that, in the view of either the investigator or Sponsor, places the patient at immediate risk of death. It does not include an AE or SAR that, had it occurred in a more severe form, might have caused death.
- Unexpected AE or unexpected SAR is an AE or SAR that is not listed in the investigator brochure or is not listed at the specificity or severity that has been observed. For example, under this definition, hepatic necrosis would be unexpected (by virtue of greater severity) if the investigator brochure referred only to elevated hepatic enzymes or hepatitis. Similarly, cerebral thromboembolism and cerebral vasculitis would be unexpected (by virtue of greater specificity) if the investigator brochure listed only cerebral vascular accidents. "Unexpected", as used in this definition, also refers to AEs or SARs that are mentioned in the investigator brochure as occurring with a class of drugs or as anticipated from the pharmacologic properties of the drug, but are not specifically mentioned as occurring with the particular drug under investigation.

#### 8.4 Documentation

All TEAEs occurring during the course of the study, whether or not considered related to the study drug or to underlying disease, must be individually recorded in the eCRF, including the nature of the event, date and time of onset (where appropriate), duration of effect, action taken, seriousness, severity, and relationship to study medication. Any consequent change to the dosage schedule or corrective therapy should be recorded.

Every attempt should be made to describe the TEAE in terms of a diagnosis. If a clear diagnosis has been made, individual signs and symptoms will not be recorded. If a clear diagnosis cannot be established, each sign and symptom must be recorded individually.

All patients who experience a TEAE, regardless of the relationship to study treatment, must be monitored to determine the outcome. The clinical course of the AE will be followed up even after the end of the period of observation for related TEAEs, until a satisfactory explanation is found or the investigator considers it medically justifiable to terminate follow-up. Should the AE result in death, a post-mortem examination should be considered as far as possible.

After last study treatment administration, patients will be observed for at least 30 days to document any late side effects and until resolution in cases of TEAEs for which a relationship to OTX015/MK-8628 cannot definitely be excluded.

AEs already recorded and designated as "continuing" should be reviewed at each subsequent assessment. If resolved, details are to be recorded in the eCRF. If an AE worsens in frequency of attacks/symptoms or in severity, a new record of the event must be started (i.e., distinct AE reports are required for differing frequencies and/or severity of the same event to enable comprehensive safety reports and later analysis).

Diagnostic and therapeutic non-invasive and invasive procedures, such as surgery, must be reported under "concomitant procedures" in the eCRF and not as an AE. The medical condition for which the procedure was performed must be reported.

#### 8.5 Grade and Severity

All AEs, whether or not they are considered related to the study drug, must be graded using the NCI Common Toxicity Criteria for Adverse Events (CTCAE) Version 4.03, which can be found at: http://evs.nci.nih.gov/ftp1/CTCAE/CTCAE\_4.03\_2010-06-14\_QuickReference\_8.5x11.pdf. The worst grade is to be documented.

AE grades usually reflect their severity, with grade 1 meaning "mild", grade 2 meaning "moderate", grade 3 meaning "severe", grade 4 meaning "life-threatening" and grade 5 meaning "fatal".

The term "severity" is used to describe the **intensity** of an AE; the event itself, however, may be of relatively minor clinical significance (e.g., 'severe' headache). This is **not** the same as "serious". Seriousness of AEs is based on the outcome/action of an AE and usually is associated with events that pose a threat to a patient's life or functioning.

Intensity of the AE will be evaluated using the following criteria:

[figure not shown]
- Mild: The patient is aware of the sign or symptom, but finds it easily tolerated. The event is of little concern to the patient and of little clinical significance. The event is not expected to have any effects on the patient's overall health or wellbeing.
- **Moderate:** The patient has discomfort enough to cause interference with or change in usual activities. The event is of some concern to the patient's health or wellbeing and may require medical intervention and/or close follow-up.
- **Severe:** The AE interferes considerably with the patient's usual activities. The event is of definite concern to the patient and/or poses substantial risk to the patient's health or wellbeing. The event is likely to require medical intervention and/or close follow-up and may be incapacitating or life-threatening. Hospitalization and treatment may be required.

# **8.6** Relationship to Study Treatment

All TEAEs occurring during treatment with an investigational agent may be related to the investigational agent. All TEAEs, regardless of the supposed relationship to study treatment, must therefore be collected. However, the investigator often has arguments to think that a TEAE is or is not related to the study treatment. Albeit subjective, and susceptible to be challenged, the assessment of relationship to study treatment is an important role of the investigator. Thus, the investigators should decide, based on their knowledge and medical expertise, whether, in their opinion, an AE is "reasonably related" or "unlikely related" to the study treatment (or to study specific procedures).

# 8.7 SAE Reporting

SAEs and other AEs that fulfill a reason for expedited reporting to Pharmacovigilance (overdose and pregnancy) must be documented on a Serious Adverse Event Report Form (SAERF) at the time the SAE is detected. This form must be completed and sent within 24 hours or at the latest on the following working day to the Sponsor's Pharmacovigilance representative:

The SAERF and guidelines for completing it are provided in the Investigator Study File. The Sponsor is responsible for ensuring that all legal reporting requirements are met.

The initial report must be as complete as possible, including details of the current illness and AE(s), and an assessment of the causal relationship between the event(s) and the investigational product.

Information not available at the time of the initial report (e.g., an AE end date or laboratory values received after the report) must be documented on a follow-up SAERF.

#### 8.8 Period of Observation

For the purposes of this study, the period of observation for collection of AEs extends from the start of treatment with the investigational product until the end of study treatment period, 30 days after the last study drug administration, except for TEAEs for which a relationship to OTX015/MK-8628 cannot definitely be excluded, which must be reported during follow-up until resolution or change of causality from related to non-related or initiation of further antitumor therapy.

If the investigator detects an SAE after the end of the period of observation, and considers the event possibly related to prior study treatment, he/she should contact the Sponsor to determine how the AE should be documented and reported.

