#### **Dose Escalation Part**

This step is designed to determine the maximum tolerated dose (MTD) in each of the two regimens, which will be evaluated in parallel. Patients will receive oral OTX015/MK-8628 according to:

Regimen 1: continuous, once daily for 21 consecutive days (21-day cycles).

Or

Regimen 2: once daily on days 1 to 7, repeated every three weeks (21-day cycles; 1 week ON/2 weeks OFF). Patients will be sequentially assigned to Regimen 1 or Regimen 2 according to the next available place and receive OTX015/MK-8628 at escalating doses levels (DL). Cohorts of 3 patients will be treated, and an additional 3 patients will be treated at the first indication of dose-limiting toxicity (DLT). MTD assessment will be based on the tolerability observed during the first 21 days of treatment.

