# Regimen 2: Days 1-7, every 21 days

A starting dose of 100 mg OTX015 administered orally once daily for 7 consecutive days, repeated every 3 weeks will be explored in an attempt to determine if discontinuous drug administration can reduce:

- 1) The incidence and severity of thrombocytopenia which appears to be the most common toxicity of OTX015 in patients with hematologic malignancies, emerging at ≥ 80 mg daily continuous dose after nearly 2 weeks of treatment exposure (grade 3-4 thrombocytopenia occurred in 50% of patients with 28% having a grade 4), with an incidence/severity appearing to increase with dose suggesting a possible schedule-dependency.
- 2) Given that in the ongoing phase I study in patients with advanced hematologic malignancies, severe thrombocytopenia tends to occur after approximately 2 weeks of continuous treatment, and that furthermore a recovery interval of approximately 10 days is required for severe thrombocytopenia to return to lower grades, a discontinuous regimen may be required to allow re-treatment every 3 weeks. This is important to take into account for future combination clinical studies.

These two regimens (with or without recovery period) will be tested in parallel, i.e., Regimen 1 (daily continuous dosing) and Regimen 2 (7 days every 21 days). This will allow selection of the optimal regimen for further studies in terms of balance between tolerability, pharmacokinetics and antitumor activity.

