2.6 Statistical Methods

The study is designed to assess the safety of OTX015/MK-8628 in patients with solid tumors. The small numbers per cohort are not intended for statistical hypotheses.

Quantitative variables will be summarized using descriptive statistics; continuous variables will be presented as N, mean and/or median, standard deviation, range, and categorical variables will be presented using frequencies and percentage. For CRPC patients, since no response was observed, waterfall plots will not be prepared.

Patient disposition and demographics will be analyzed in all included patients, response will be analyzed in patients evaluable for efficacy, and safety will be analyzed in the treated population with an additional analysis in patients evaluable for DLT.

AEs will be coded according to the most recent version of the Medical Dictionary for Regulatory Activities (MedDRA) and will be tabulated by System Organ Class and Preferred Term. Laboratory values outside normal limits will be summarized using the NCI-CTCAE version 4.03. Concomitant medications will be coded according to the WHO Drug Dictionary.

Data will be presented by dose level, regimen, and where appropriate by indication. No imputations for missing data will be made.

Pharmacokinetics and pharmacodynamics will be analyzed and reported separately.

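### The 30-days-from-last-intake window closes up to 14 days sooner in Regimen 2, so crude percentages of all-cause AEs, SAEs and deaths slightly favour that regimen

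*Protocol*

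**What the plan says.** Protocol 8.8 collects AEs from the start of treatment "until the end of study treatment period, 30 days after the last study drug administration". TEAEs that may be related are an exception, "which must be reported during follow-up until resolution or change of causality from related to non-related or initiation of further antitumor therapy". A possibly related SAE found after the window is referred to the Sponsor.

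Protocol 8.3 makes any death on study, or within 30 days of the last dose, an SAE: "all deaths occurring within 30 days of the last administration of study drug must be managed as SAEs and reported as such". Related deaths count at any interval. The same section limits a TEAE to a sign, symptom, syndrome or "illness that develops or worsens during the period of observation in the clinical study".

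Two further windows share the anchor. The final visit is 35 ± 5 days after the last intake (Protocol 7.3), and events of clinical interest are reported to 30 days after treatment stops (Protocol 8.9).

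Both regimens use 21-day cycles. Regimen 1 doses on every day of the cycle and Regimen 2 on days 1 to 7 (Protocol synopsis and 3.1).

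Safety is analysed in the treated population and presented by dose level and regimen. Under SAP 2.6, "categorical variables will be presented using frequencies and percentage"; Protocol 11.4 plans the same. Neither document plans a summary adjusted for exposure or follow-up. Protocol 1.4.2 says of running the two regimens in parallel: "This will allow selection of the optimal regimen for further studies in terms of balance between tolerability, pharmacokinetics and antitumor activity".

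**The concern.** A window tied to the last capsule gives both regimens the same time off drug, but not the same total time under observation. A patient who completes a cycle in Regimen 2 has already used 14 of the 30 days when the cycle ends. The matching Regimen 1 patient has used none.

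AE and SAE incidence by regimen are secondary endpoints (Protocol 11.2, SAP 2.4), and tolerability is one of the stated grounds for choosing between regimens. A crude percentage over a shorter window is lower even if the underlying rates are identical. The direction is known in advance and always favours Regimen 2.

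**Working it through.** **Inputs.** Cycle length is 21 days; the last dosing day is 21 in Regimen 1 and 7 in Regimen 2 (synopsis, 3.1). The window runs 30 days from the last intake (8.3, 8.8). There are up to 24 patients per regimen (11.1). Assumed range for median survival: 6.7 months (NUT midline carcinoma, 1.2.1) to 12 months (advanced TNBC, 1.2.3).

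**The plan's own figure.** Off-drug days per Regimen 2 cycle: 21 − 7 = 14, which matches the stated 2 weeks OFF.

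**Day the window closes after k completed, unmodified cycles.**
- Regimen 1: 21k + 30
- Regimen 2: 21(k − 1) + 7 + 30 = 21k + 16

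| k | Regimen 1 | Regimen 2 | Gap | Gap ÷ Regimen 1 |
|---|---|---|---|---|
| 1 | 51 | 37 | 14 | 27.5% |
| 2 | 72 | 58 | 14 | 19.4% |
| 4 | 114 | 100 | 14 | 12.3% |
| 6 | 156 | 142 | 14 | 9.0% |

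The last column is the shortening in time, not in events. The median was 2 cycles in both cohorts of the hematologic study (Tables 4 and 5), so the upper rows are the relevant ones.

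**The final visit does not close the gap.** It falls on day 21k + 35 against 21k + 21, again 14 days apart.

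**When the gap is smaller.** If both patients stop on cycle day d, the gap is max(0, d − 7): 0 for a stop by day 7, 7 on day 14, 11 on day 18. A Regimen 1 patient moved to 2 weeks ON/1 week OFF (5.2.7) takes the last dose of a cycle on day 14, so the gap is 14 − 7 = 7 days. If both patients take the first dose of cycle 3 (day 43) before the scan leads to a stop, both windows close on day 43 + 30 = 73 and the gap is 0.

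**Illustration for all-cause deaths.** The same constant hazard is assumed in both regimens, with 30.4375 days per month. Captured share = 1 − exp(−ln 2 × days ÷ median).

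| Median | k | Regimen 1 | Regimen 2 | Difference, points | Deaths per 24 |
|---|---|---|---|---|---|
| 6.7 months | 1 | 15.9% | 11.8% | 4.1 | 0.98 |
| 6.7 months | 2 | 21.7% | 17.9% | 3.8 | 0.92 |
| 12 months | 1 | 9.2% | 6.8% | 2.4 | 0.59 |
| 12 months | 2 | 12.8% | 10.4% | 2.3 | 0.56 |

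**Every started cycle is fully observed.** Even if the only dose of a cycle is taken on its day 1, the window runs to day 1 + 30 = 31 of that cycle, beyond day 21. This holds in both regimens, so the loss lies wholly in the tail after treatment.

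**The case against.** The strongest reply is that off-drug observation is equal, at 30 days in both regimens. The Regimen 2 days not covered are days 31 to 44 after the last dose. The longest half-life in the hematologic study was 5.7 hours (Pharmacokinetic Findings), so 30 days is 30 × 24 ÷ 5.7 = 126 half-lives. Platelets there usually recovered within 10 days of interruption. Little direct drug toxicity should be missed, and this stands. There is one caution: Protocol 5.2.4 warns that drug-induced liver injury can develop after the drug is stopped.

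Related events also have their own protection: deaths at any interval, TEAEs followed to resolution, and late SAEs referred to the Sponsor. That stands for deaths and for events already under way. It is weaker for new ones, since a TEAE must begin or worsen within the window and a late SAE is not captured automatically.

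The limit is also softer than it looks, because follow-up is for at least 30 days (8.4) and deaths on study count. But the final visit is tied to last intake too, so this does not remove the gap.

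Finally, the comparison is descriptive and non-randomized, across different dose levels, with no hypotheses intended. That limits the weight of any regimen contrast; it does not justify leaving in a bias of known direction.

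A reader might infer that 12 to 27% of Regimen 1's events would go uncounted in Regimen 2. The documents do not support that. It needs a constant event rate through the off-drug tail, and the planned summaries count patients, so percentages level off once most patients have had an event.

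**Conclusion.** The limitation is real but small, and confined to all-cause tables. For completed, unmodified cycles the Regimen 2 window is exactly 14 days shorter; that is the maximum, and many actual stops will give less. What is lost is mainly disease-related or unrelated late events and all-cause deaths. The size given for deaths rests on an equal, constant hazard and on two survival medians borrowed from the background sections, so it is an assumed range and not a forecast. The documents give no background AE rate from which to size the effect on AEs.

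A reader might go further and conclude that Regimen 2 will look safer overall, or that the MTD is biased. Neither follows. DLT is counted over days 1 to 21 in both regimens (Protocol 11.2, SAP 2.4), so the dose-finding result is untouched, and nothing shows a material effect on drug-related toxicity.

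**What to change.** Amend SAP 2.6 as follows.

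1. Keep the planned 30-day tables, with a footnote that the window from first dose is up to 14 days shorter in Regimen 2.
2. Base any between-regimen comparison of all-cause AEs, SAEs and deaths on incidence by cycle: patients with an event in days 1 to 21 of the cycle, over patients who started it. A common window from first dose is an alternative. Days 1 to 31 would be covered for every treated patient, barring death or withdrawal of consent.
3. Events per patient-time may be added as a supportive table with the constant-rate assumption stated. It should not stand alone: if the rate falls after treatment stops, the 14 extra tail days dilute Regimen 1's rate and over-correct.

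Two changes are not needed. Discontinuations due to AEs can stay as planned, because a patient already off drug cannot discontinue it. Extending capture in Protocol 8.3 and 8.8 would give Regimen 2 patients 30 + 14 = 44 off-drug days against 30. It would also probably come too late, since SAP 2.2 describes Regimens 1 and 2 in the past tense and SAP 2.6 already reports that no CRPC response was seen.

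The cost is a few extra descriptive tables from dosing and onset dates already collected. Per-cycle tables leave the post-treatment tail out of the comparison, and later cycles include only patients still on treatment; the 30-day tables continue to show the tail.
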